2.2 Rationale

Children, adolescents and young adults undergoing major surgery are frequently exposed to a high risk of perioperative bleeding with concomitant requirement of blood product transfusion. This increases the risk of postoperative adverse outcomes, resulting in longer length of hospital stay and increased morbidity and mortality. The underlying mechanisms that increase the bleeding risk differ depending on the type of surgery performed. Increased fibrinolysis has been implicated as a contributing factor in excessive blood loss in pediatric spinal surgery, adult arthroplasty (TKA) and other major surgeries. Studies utilizing TXA in pediatric orthopedic surgery support its use to reduce perioperative blood loss, drain output and post-operative hematoma. 1,2,11,15

Because of the significant risks and complications associated with blood loss and allogenic transfusions, efforts to identify safe and effective ways of minimizing blood loss perioperatively are crucial. Reducing blood loss and transfusion needs minimizes post-operative complications, hospital stay length, and decreases risk of development of transfusion related complications such as allergic or transfusion reactions, transfusion-related acute lung injury (TRALI), or risk of transmission of blood borne illness^{18,19}.

Maintaining a nearer to normal Hgb and Hct allows the patient to undergo more aggressive physical therapy sooner. Higher postoperative Hgb and Hct levels promote improved wound healing as well. The use of antifibrinolytic drugs will help to improve clinical care and functional outcome of children undergoing limb salvage operations.

The administration of antifibrinolitics, such as TXA and EACA, has been shown to reduce bleeding in various surgeries including cardiac, trauma, hip, and knee arthroplasty, gynecological, and urologic procedures in adolescents and young adults.^{1,2} Since January of 2014 to December of 2017, 39 patients at our institution underwent limb-sparing tumor resections of the proximal tibia or distal femur that met the inclusion criteria for our proposed study. All 39 patients received either an intraoperative or postoperative blood transfusion. The average total blood volume transfused was 19.78 mL/kg with a standard deviation of 11.38 mL/kg. The average number of transfusions received was 2.95 with a standard deviation of 1.83. The average Estimated Blood Loss per Kilogram of Body Weight was 17.84 mL/kg with a standard deviation of 16.28 mL/kg.

2.3 Background and Rationale for Ancillary and Exploratory Studies

ROTEM® is an established viscoelastic measurement of hemostasis of whole blood at low shear forces. The results of a ROTEM are reported as a reaction curve which shows the elasticity over time when a blood clot forms and dissolves. The measurement parameters available are as follows:

- CT (Clotting time): The CT is the latency time from adding the start reagent to blood until the clot starts to form.
- CFT (Clot formation time) and alpha-angle: The alpha angle is the angle of

tangent between the curve while CFT is the time from CT until a clot firmness of 20 mm point has been reached. These parameters denote the speed at which a solid clot forms and are primarily influenced by platelet, fibrinogen and coagulation factors.

- MCF (Maximum clot firmness): MCF is the greatest vertical amplitude of the trace. It reflects the absolute strength of the fibrin and platelet clot.
- A10 and A20 values: These values describe the clot firmness (or amplitude) obtained after 10 and 20 minutes and provide a forecast on the expected MCF value at an earlier stage already.
- LI 30 (Lysis Index after 30 minutes) and ML (Maximum Lysis): The LI30 value is the percentage of remaining clot stability in relation to the MCF value at 30 min after CT. The ML parameter describes the percentage of lost clot stability (relative to MCF, in %) viewed at any selected time point or when the test has been stopped. A low LI (X) value or a high ML value indicates hyperfibrinolysis. While in normal blood fibrinolysis activity is quite low, in clinical samples a more rapid loss of clot stability by hyperfibrinolysis may lead to bleeding complications which can be treated by the administration of antifibrinolytic drugs.

Of particular interest for this randomized trial will be the association with the LI30 to EBL, transfusion requirements and clinical outcomes, because the addition of an antifibrinolytic agent like TXA should have a direct impact on this value.

3. RESEARCH PARTICIPANT ELIGIBILITY CRITERIA AND STUDY ENROLLMENT

According to institutional and NIH policy, the study will accession research participants regardless of gender and ethnic background. Institutional experience confirms broad representation in this regard.

All clinical and laboratory studies to determine eligibility must be performed within 7 days prior to enrollment unless otherwise indicated. Laboratory values used to assess eligibility must be no older than 7 days at the start of therapy. If a post-enrollment lab

value is outside the limits of eligibility, or laboratory values are > 7 days old, then the following laboratory evaluations must be re-checked within 72 hours prior to initiating therapy: CBC with differential, PT, PTT, INR, Fibrinogen, Pregnancy Test and Comprehensive Metabolic Panel (CMP).

3.1. Inclusion Criteria

3.1.1. Participant undergoing limb salvage procedure of malignant bone tumor of the distal femur or proximal tibia, which typically requires blood transfusions.

3.1.2. Patient under the age of 25

3.1.3. Organ Function Requirements:

a. Adequate bone marrow function defined as:

- Upward trending peripheral absolute neutrophil count (ANC)
- Platelet count $\geq 100,000/\text{mm}^3$ (transfusion independent defined as no platelets required for 4 days)
- Hemoglobin $\geq 8.0 \text{ g/dL}$
- No RBC transfusion within 24 hours

b. Adequate renal function defined as:

- Creatinine clearance or radioisotope GFR $\geq 70 \text{ mL/min}/1.73\text{m}^2$
OR

Maximum Serum creatinine based on age/gender as follows: (threshold creatinine values were derived from the Schwartz formula for estimating GFR) (Schwartz GJ, Gauthier B. J Pediatr 1985; 106: 522-6)

Age	Maximum Serum Creatinine (mg/dL)	
	Male	Female
1 day to < 1 years	0.6	0.5
1 to < 2 years	0.6	0.6
2 to < 6 years	0.8	0.8
6 to < 10 years	1.0	1.0
10 to < 13 years	1.2	1.2
13 to < 16 years	1.5	1.4
≥ 16 years	1.7	1.4

c. Adequate liver function defined as:

- Total bilirubin $\leq 1.5 \times$ the institutional upper limit of normal (IULN) for age
- ALT (SGPT) and AST (SGOT) $\leq 2.5 \times$ IULN for age (or $< 5 \times$ IULN for patients with documented disease involving the liver or $10 \times$ IULN for patients receiving HDMTX)
- Serum albumin $> 2 \text{ g/dL}$

d. Adequate coagulation function as defined by International Normalized Ratio (INR) ≤ 1.5

3.1.4 Female participants of child-bearing potential (> 10 years old) must have a negative serum or urine pregnancy test within 72 hours of sedation

3.2. Exclusion Criteria

- 3.2.1. Participants whose limb salvage procedure may require significant manipulation of major blood vessels.
- 3.2.2. Participants with known bone marrow deficiency resulting in red blood cell deficiency (e.g. Diamond-Blackfan anemia)
- 3.2.3. Participants receiving erythropoietin-stimulating agents (e.g. epoetin alfa)
- 3.2.4. Participants with active hemorrhagic cystitis (e.g. alkylator-induced) with gross hematuria or >50 RBCs per high powered field on urinalysis
- 3.2.5. Participants actively receiving all-trans retinoic acid (ATRA) or isotretinoin (Accutane)
- 3.2.6. Participants with known allergies to antifibrinolytics
- 3.2.7. Participants with known hypercoagulopathies
- 3.2.8. Personal history of a thrombosis or active thrombus
- 3.2.9. Participants currently on anticoagulation medications (e.g. warfarin, enoxaparin)
- 3.2.10. Participants with a history of seizures. Patients with a history of febrile seizure are eligible.
- 3.2.11. Persisting toxicity related to other systemic therapies (e.g. chemotherapy) which constitutes an unacceptable safety risk based on the judgment of the PI and/or the primary treating physician
- 3.2.12. Female participants who are currently pregnant or actively breastfeeding.
- 3.2.13. Female participants who are currently receiving estrogen-based contraception therapy.
- 3.2.14. Inability or unwillingness of research participant or legal guardian/representative to give written informed consent.
- 3.2.15. Participants enrolled in another clinical trial utilizing an IND/IDE experimental therapy.
- 3.2.16. Participants with a history of CNS disease.
- 3.2.17. Participants with known bleeding disorder.
- 3.2.18. Participants with known platelet dysfunction.

3.3 Research Participant Recruitment and Screening

This clinical trial will be conducted solely at St. Jude Children's Research Hospital (SJCRH). Recruitment will begin in Year 1 and will be completed when a total accrual of 39 limb salvage patients (to yield 38 evaluable subjects) is reached. Subjects will be approached and enrolled during regular surgery consult visits when surgery is being planned. We plan on approaching all available eligible participants until enrollment is completed. The study will be discussed with each potentially eligible family by the PI and/or designee in an unbiased basis until enrollment goals are met.

3.4. Enrollment on Study at St. Jude

A member of the study team will confirm potential participant eligibility as defined in Section 3.1 -3.2, complete and sign the 'Participant Eligibility Checklist'. The completed

checklist will be faxed to Clinical Trials Operations at [REDACTED]; followed by a phone call to [REDACTED] to ensure that the fax is received. Eligibility will be reviewed and entered into the Clinical Trials Management System. A research participant-specific consent form and assent document, where applicable, will be generated. The signed consent/assent form must be faxed or emailed to Clinical Trials Operations (CTO) at [REDACTED] in order to complete the enrollment. To assist with enrollments and consent release, the Clinical Trials Operations (CTO) staff is available Monday through Friday. After hours and on weekends and holidays, the study team is referred to the CTO webpage for additional resources and instructions. Link: [REDACTED]

3.5. Procedures for Identifying and Randomizing Research Participants

Prior to initiating the study, a workshop will be held at SJCRH with team members participating. The background to the study, study procedures, consent processes, data transfer, and plans to monitor intervention integrity and data quality will be the content for that workshop.

Following the workshop and preparation for data collection, screening for eligible research participants will begin. Eligibility of newly admitted research participants will be confirmed during daily discussions between the PI, designee, and attending physician. The PI or designee will then approach the parent or participant regarding the study and only after the parent/participant has given permission for such will the PI or designee discuss the study with the research participant. If both the research participant and parent agree to participate, the randomization plan established by the study biostatistician will be accessed according to Section 11.1.

4. TREATMENT PLAN

4.1 Study Treatment

Upon participant enrollment, a SJCRH Pharmaceutical Services Department pharmacist will randomize each participant to one of two possible treatment arms (see section 11 for randomization).

To allow for the study team and participants to remain blinded to the treatment assignment, the study drug will be labeled as Tranexamic Acid/Placebo (TXAKIDS) followed by applicable dose and administration instructions.

Study treatment order entry will be managed by study staff according to protocol and institutional policies for medication administration. Any modifications to the study treatment (frequency or discontinuation) will be done by the study team.

4.1.1. Active Treatment Arm

At initiation of surgical preparation, participants randomized to the active treatment arm will receive tranexamic acid 10 mg/kg (max 1 g), given via syringe pump programmed to infuse over 15 minutes. If infused over 15 minutes, the maximum possible rate will be 67 mg/min (for the maximum 1g dose).

4.1.2. Placebo Treatment Arm

At initiation of surgical preparation, participants randomized to the placebo treatment arm will receive 0.9% sodium chloride. It will be matched in appearance, volume, and administration to the active treatment arm with tranexamic acid.

4.1.3 Second Dose

If no unacceptable toxicities occur, a second dose of tranexamic acid/placebo (TXAKIDS) 10 mg/kg (max 1 g) IV push over 5 to 15 minutes will be given 6 hours (with a window of +/- 30 minutes) after the first dose (either intra- or post-operatively).

4.2. Dose Modifications

4.2.1. Check BUN/serum creatinine on post-op day 3.

4.2.2. If the patient has a seizure after the first dose and prior to the second dose, the second dose will not be given.

4.2.3. An anaphylactic reaction will be considered if the patient experiences any of the following 2 symptoms during infusion: nausea/vomiting; hives, pruritis or angioedema; dyspnea, wheezing or hypoxemia; syncope; or incontinence. A sudden decrease in systolic blood pressure by >30% based on age will also be considered evidence of anaphylaxis.

4.2.3.1. In case of anaphylactic reaction, immediately discontinue infusion of study agent.

4.2.3.2. Administer diphenhydramine 1 mg/kg IV (max dose 50 mg) and epinephrine 1 mg/ml (1:1000) 0.01 mg/kg IM, max dose 0.5 mg.

4.2.3.3. Additional supportive care including oxygen, bronchodilators, steroid and vasopressor support may be administered as appropriate.

4.2.3.4. The anesthesia provider will monitor continuously for signs of allergic reaction. These signs may include bronchospasm (increased airway pressures, difficulty with ventilation), and/or skin rash. Hypotension and tachycardia can be seen when an allergic reaction progresses to anaphylactic shock and may be suspected for hypotension unresponsive to fluid bolus. If an allergic reaction is suspected, a serum tryptase level will be drawn, while

treatment for allergic reaction (i.e., Epinephrine, anti-histamines) is commenced.

4.2.3.5. Medication Hypersensitivity and Anaphylaxis Treatment Guidelines can be found at:

4.3. Concomitant Therapy

4.3.1. Non- Allowed Concomitant Therapies

4.3.1.1. Herbal remedies that may impact coagulation (e.g. St. John's Wort) or have unknown effects on coagulation.

4.3.2. Allowed Concomitant Therapies

4.3.2.1. Patients may receive systemic therapies in accordance with their diagnosis, i.e., chemotherapy for patients with malignancy.

4.3.2.2. Patients with a history of reactions to transfusions may receive appropriate pre-medications (e.g. acetaminophen, diphenhydramine).

4.3.2.3. Medications that cause temporary impairment of platelet function should be used with caution.

4.3.2.4. All concomitant and supportive care medications should be documented.

4.3.3. NSAIDS will be given per standard postoperative pain protocol which is immediately after surgery.

4.4. Supportive Care

4.4.1. Central Venous Catheter

While not required for the purposes of this study, many participants will have a central venous catheter/line (CVL) in place for intravenous (IV) administration of medications and blood products. The CVL may be used for administration of the investigational agent/placebo as well as for blood draws, transfusions and other needs based on best medical practice.

It is possible that the risk of forming a blood clot in a deep vein or developing problems with the central line function may be higher than expected in the group that receives TXA. The children in this study are at higher risk of these complications than people in previous studies using TXA because of their cancer diagnosis and the fact that they may have a central venous line.

4.4.2. Additional Post-Operative Supportive Cares

Participants will receive standard post-operative supportive measures including IV hydration, pain medications, nutritional supplementation, and antibiotics per standard procedures as indicated by the responsible members of Surgery, Anesthesiology, Critical Care, and the primary treating service.

5. DRUG INFORMATION

5.1 Tranexamic Acid (Cykloapron®)

Source and Pharmacology: Tranexamic acid is antifibrinolytic, antihemophilic and hemostatic agent that forms a reversible complex that displaces plasminogen from fibrin resulting in inhibition of fibrinolysis. It also inhibits the proteolytic activity of plasmin. By reducing plasmin activity, tranexamic acid also reduces activation of complement and consumption of C1 esterase inhibitor (C1-INH), thereby decreasing inflammation associated with hereditary angioedema.

Formulation and Stability: Tranexamic acid is available as an intravenous solution at a concentration of 1000mg/10mL (10mL vial). Room temperature storage is recommended (25°C or 77°F, with temperature excursions permitted from 15°C to 30°C (59°F to 86°F)).

Supplier: Commercially available from Pfizer as Cykloapron® or generic manufacturers.

Toxicity: Adverse reactions associated with the injection of Tranexamic acid include (frequency not defined): hypotension with rapid IV injection (>1 mL per minute), dizziness, allergic dermatitis, menstrual disease (unusual menstrual discomfort), diarrhea, nausea, vomiting, and blurred vision. Adverse reactions seen with all formulations that were observed to be rare (< 1%), through post marketing, and/or case reports include: allergic skin reaction, anaphylactic shock, anaphylactoid reaction, cerebral thrombosis, deep vein thrombosis, diarrhea, dizziness, nausea, pulmonary embolism, renal cortical necrosis, retinal artery occlusion, retinal vein occlusion, seizure, ureteral obstruction, visual disturbances (including impaired color vision and vision loss), and vomiting.

Dosage and route of administration including infusion times: The first dose will be given at initiation of surgical preparation, and the second dose will be given 6 hours after the first dose (either intra- or post-operatively). Dose will be given by intravenous push over 5 to 15 minutes at 10mg/kg with a maximum dose of 1 g. Dose will not be injected more rapidly than 1 mL per minute to prevent hypotension.

Dose rounding at St. Jude will be allowed according to institutional policy (See St. Jude Institutional Policy 20.03.004).

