APPENDIX IV: RESEARCH TESTS

Research Test	Pre-Study	During Study	End of Study
ROTEM	No	In PACU, required	No
Tranexamic acid (TXA)	No	1 IV dose over 5 to 15 minutes; second IV dose over 5 to 15 minutes to be given 6 hours later if serum creatinine level has not doubled	No

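### Sections 4.1.1, 4.1.3, 5.1 and Appendix IV disagree on how study drug is given; at the stated 100 mg/mL, the 5-minute lower bound breaks the section 5.1 rate limit above 50 kg

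*Combined protocol and SAP*

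**What the plan says.** Four places in the combined protocol and SAP tell staff how to give the study drug.

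- **Section 4.1.1 (first dose, active arm):** "given via syringe pump programmed to infuse over 15 minutes". It adds that at this duration "the maximum possible rate will be 67 mg/min (for the maximum 1g dose").
- **Section 4.1.3 (second dose):** "10 mg/kg (max 1 g) IV push over 5 to 15 minutes". It gives no limit in mL/min and no cross-reference to section 5.1.
- **Section 5.1 (first and second doses described together):** "Dose will be given by intravenous push over 5 to 15 minutes", at 10 mg/kg up to 1 g, followed by "Dose will not be injected more rapidly than 1 mL per minute to prevent hypotension". Its toxicity paragraph gives the reason by listing "hypotension with rapid IV injection (>1 mL per minute"). Its formulation paragraph says "Tranexamic acid is available as an intravenous solution at a concentration of 1000mg/10mL (10mL vial").
- **Appendix IV (research tests):** "1 IV dose over 5 to 15 minutes", and the same range for the second dose. It states no rate limit. It does not repeat the dose either, but the treatment outline in the synopsis applies 10 mg/kg with a 1 g maximum to all doses.

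Sections 4.1.2 and 5.2 match the placebo to the active arm in how it is administered.

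**The concern.** There are two separate discrepancies.

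1. **Duration against rate.** The dose rises with weight, but the shortest permitted duration stays at 5 minutes. Above some weight, a 5-minute administration must exceed a fixed limit in mL/min. Section 5.1 puts the range and the limit side by side, so its reader is warned. The reader of section 4.1.3 or Appendix IV is not.
2. **Method for the first dose.** Section 4.1.1 specifies a pump and one duration. Section 5.1 specifies a push and a range of durations, and Appendix IV gives the range with no method beyond the intravenous route.

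What is at stake is patient safety. The protocol itself names hypotension as the harm that the limit is meant to prevent. Under section 4.1, orders are entered according to the protocol and institutional policy, and the label carries administration instructions. Which section the order is built from may therefore decide whether the limit reaches the bedside. Because placebo is matched on administration, the same unclear text governs both arms. I claim no effect on sample size, endpoints or analysis.

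**Working it through.** **Inputs**

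- Dose 10 mg/kg, maximum 1,000 mg (synopsis, 4.1.1, 4.1.3, 5.1).
- Concentration 1,000 mg / 10 mL = 100 mg/mL (5.1). This is the product as supplied; the concentration as given is not stated, so using 100 mg/mL is an assumption.
- Rate limit 1 mL/min (5.1).
- Durations: 15 minutes (4.1.1); 5 to 15 minutes (4.1.3, 5.1, Appendix IV).
- Historical median pre-operative weight 45.2 kg (11.1); 39 historical patients (2.2, 11.2.2).

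**Step 1: the plan's own figure.** 1,000 mg / 15 min = 66.7 mg/min, which rounds to the 67 mg/min in section 4.1.1. In volume, 66.7 / 100 = 0.67 mL/min, inside the section 5.1 limit. Section 4.1.1 therefore meets both the duration and the rate in section 5.1.

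**Step 2: volume.** 10 mg/kg / 100 mg/mL = 0.1 mL/kg, up to 1,000 / 100 = 10 mL, reached at 100 kg.

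**Step 3: weight at which 5 minutes reaches the limit.** 5 min × 1 mL/min / 0.1 mL/kg = 50 kg.

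**Step 4: rates across weight.** Rate over 5 minutes = volume / 5. The shortest time within the limit, in minutes, equals the volume in mL.

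| Weight | Volume (mL) | Rate over 5 min (mL/min) | Shortest time at 1 mL/min (min) |
|---|---|---|---|
| 45.2 kg | 4.52 | 0.90 | 4.52 |
| 50 kg | 5 | 1.0 | 5 |
| 60 kg | 6 | 1.2 | 6 |
| 80 kg | 8 | 1.6 | 8 |
| 100 kg or more | 10 | 2.0 | 10 |

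At the 1 g maximum, 5 minutes means 1,000 / 5 = 200 mg/min. That is twice the section 5.1 limit (100 mg/min at this concentration) and 200 / 67 ≈ 3 times the maximum rate quoted in section 4.1.1.

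**Step 5: sensitivity to concentration.** The limit is in mL/min, so dilution makes it bind sooner. At 50 mg/mL the 5-minute threshold is 5 × 1 × 50 / 10 = 25 kg; at 20 mg/mL it is 5 × 1 × 20 / 10 = 10 kg. At 50 mg/mL, 1 g is 20 mL, and even 15 minutes gives 20 / 15 = 1.33 mL/min. Among these concentrations, 100 mg/mL is the lenient case.

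**Step 6: how many patients.** The documents give no share above 50 kg. If the 45.2 kg median comes from the same 39 patients, it is the 20th ordered value, so at most 19 exceed it. The number above 50 kg then lies between 0 and 19 of 39 (0 to 49%).

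**Step 7: first dose, side by side.** Section 4.1.1: syringe pump, 15 minutes. Section 5.1: push, 5 to 15 minutes, with the rate limit. Appendix IV: intravenous, 5 to 15 minutes, no rate limit. The durations overlap at 15 minutes; the method and the permitted range do not agree.

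**The case against.** The best reply is that this is silence rather than contradiction. Section 5.1 is the dosage-and-route text for both doses, and a limit stated once there can be taken to govern the whole protocol. At 100 mg/mL, its range and its limit can both be met at every weight, since 1 g over 10 to 15 minutes satisfies each. A breach requires someone to read section 4.1.3 or Appendix IV in isolation. Orders also follow institutional policy and doses are dispensed by the pharmacy; either may already impose the limit. Appendix IV is a list of research items rather than the treatment plan, and the 15-minute infusion in section 4.1.1 breaches nothing in section 5.1.

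Much of this stands. Section 5.1 is coherent by itself, section 4.1.1 fits within it on duration and rate, and no breach has been shown to have occurred. The order set, the label text and the institutional policy are not in the documents, so whether they carry the limit is unknown. The 50 kg figure depends on an assumed concentration, and the share of patients affected could be zero.

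The objection does not remove the problem. Section 4.1.3 is the treatment-plan instruction for the second dose. It expressly allows 5 minutes with up to 1 g and points nowhere else. A safety limit should not depend on staff finding it in another section or on a later check. Dilution would only lower the weight at which the conflict begins. Treating section 5.1 as controlling also leaves the pump-or-push difference for the first dose unresolved.

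**Conclusion.** The concern holds. The instructions in sections 4.1.1, 4.1.3, 5.1 and Appendix IV are inconsistent, and the lower end of the range in section 4.1.3 and Appendix IV permits a rate that section 5.1 bars. Assuming the drug is given at 100 mg/mL, the conflict begins above 50 kg and reaches twice the limit at 1 g; at a lower concentration it begins at a lower weight. Exposure is uncertain: the historical median of 45.2 kg lies just under the threshold and bounds the share above 50 kg only at 0 to 49%, if that median covers the same 39 patients. The first-dose discrepancy concerns method and permitted durations; following section 4.1.1 at 100 mg/mL causes no rate breach. Because the text is an operative safety instruction with a harm named by the protocol itself, it must be reconciled.

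**What to change.** The sponsor should reconcile sections 4.1.1, 4.1.3, 5.1 and Appendix IV so that, for each dose, the method, duration and rate agree with one another over the whole weight range. The concentration as given should be stated, because a limit in mL/min cannot be checked against a duration without it. The reconciled text should then be carried into the order entry and the label, for active drug and placebo alike. Which instruction is clinically right is for the sponsor and the responsible clinicians to decide; no view is taken here.

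The cost is wording in four places plus the order and label text. No extra patients, visits or data are needed.
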